5.7 Handling of dropouts, missing data and outliers

Outliers will be included in summary tables and listings and will not be handled separately in any analyses. All collected data, even if not tabulated, will be listed. Generally, no imputation of data will be performed. However, when calculating statistics for PK plasma concentrations, concentrations under LLOQ will be replaced with LLOQ/2 if more than 50% of the values for a given time point are above LLOQ. For figures presenting individual PK concentrations, no imputation is performed for values under LLOQ. For imputation of PK plasma concentration below LLOQ with the purpose of calculating PK parameters, see Section 9.2.1.

Safety laboratory concentrations under LLOQ will be replaced with LLOQ/2 and concentrations over ULOQ will be replaced with ULOQ for the purpose of calculating descriptive statistics.

In case of missing start and stop times of AEs that cannot be investigated further, missing data will be imputed according to a worst-case scenario, i.e., start time will be imputed as the closest time point post first intake of IMP and end time as 23:59, resulting in the longest possible treatment emergent duration of the AE.

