- λ_{dz} : /h
- Apparent Clearance: L/h
- Apparent Volume of distribution: L
- A_e : umol and/or mg

Non-compartmental analysis will be based on the actual sampling times recorded during the trial. For the purpose of calculating PK parameters, concentrations below lower limit of quantification (LLOQ) occurring before C_{max} will be treated as zero. Concentrations below LLOQ occurring after C_{max} will be omitted from the analysis.

T_{max} , T_{last} , and C_{max} will be based on the observed plasma concentration data.

All AUC will be assessed by integration of the plasma concentration vs time curve using linear interpolation for increasing plasma levels and logarithmic interpolation for decreasing plasma levels (Linear Up-Log Down method).

AUC_{0-last} will be calculated from time 0 to the time t of the last detectable plasma concentration.

For AUC_{0-inf} the area will be calculated to the last timepoint showing a measurable plasma concentration and then extrapolated to infinity using the concentration in the last quantifiable sample and λ_{dz} .

$$AUC_{0-inf} = AUC_{0-last} + \frac{C_{last}}{\lambda_{dz}}$$

Partial AUC/ AUC_{tau} will be derived according to specified time windows/dosing interval, if the end time of the interval does not occur at an actual timepoint either linear interpolation or extrapolation will be used for derivation of the partial AUC. Extrapolation, using λ_{dz} , will only be used if the end time of specified interval occur after last detectable plasma concentration.

Formulas for calculation of AUC

- Linear trapezoidal rule:

$$AUC|_{t_1}^{t_2} = \delta t \times \frac{C_1 + C_2}{2}$$

- Logarithmic trapezoidal rule:

$$AUC|_{t_1}^{t_2} = \delta t \times \frac{C_2 - C_1}{\ln\left(\frac{C_2}{C_1}\right)}$$

where t = time, c = concentration, $\delta t = t_2 - t_1$.

Formulas for interpolation (to find C^* at time t^* for $t_1 < t^* < t_2$)

- Linear interpolation rule:

$$C^* = C_1 + \left| \frac{t^* - t_1}{t_2 - t_1} \right| (C_2 - C_1)$$

- Logarithmic interpolation rule:

$$C^* = \exp \left(\ln(C_1) + \left| \frac{t^* - t_1}{t_2 - t_1} \right| * (\ln(C_2) - \ln(C_1)) \right)$$

where t = time, c = concentration

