λ_{z} , the first order rate constant associated with the terminal portion of the curve will be determined by lin-logarithmic regression of the terminal elimination phase of individual plasma concentration vs time curves. Determination of λ_{z} requires identification of a sufficiently linear terminal phase (as determined by visual inspection of the lin-log plasma concentration vs time plot with the regression line) consisting of at least 3 terminal concentration values (not including C_{\max}). If this is not achieved, λ_{z} and its dependent PK parameters will not be reported for that profile.

In the following cases, λ_{z} dependent PK parameters will be flagged in listings as potentially unreliable:

- λ_{z} estimation is based on a period of less than 1.5 times the resulting $T_{1/2}$.
- The Rsq adjusted value of the regression line is < 0.85 .
- The estimated % extrapolated AUC is $> 20\%$ $((AUC_{0-\text{inf}} - AUC_{0-\text{last}} / AUC_{0-\text{inf}}) * 100)$.

$T_{1/2}$ will be calculated accordingly:

$$T_{1/2} = \frac{\ln(2)}{\lambda_{z}}$$

Span will be calculated accordingly:

$$\text{Span} = \frac{\lambda_{z \text{ upper}} - \lambda_{z \text{ lower}}}{T_{1/2}}$$

CL will be calculated accordingly:

$$\text{Single dose: } \frac{CL}{F} = \frac{Dose}{AUC_{0-inf}} \quad \text{Steady state: } \frac{CL}{F} = \frac{Dose}{AUC_{0-tau}}$$

V_z will be calculated accordingly:

$$\text{Single dose: } \frac{V_z}{F} = \frac{Dose}{\lambda_{dz} * AUC_{0-inf}} \quad \text{Steady state: } \frac{V_z}{F} = \frac{Dose}{\lambda_{dz} * AUC_{0-tau}}$$

A_e will be calculated accordingly:

$$A_e = \sum_{i=1}^n v_i * c_i$$

Let v be the volume of urine and c the concentration of drug in urine, the product of v and c for one interval (i) represent A_e . The A_e over 0-12 hours (MAD BID), 0-24 hours (SAD 1-4) and 0-48 hours (SAD 5) is the sum of all intervals. The weight of the collected urine fractions will be calculated assuming a urine density of 1.00 g/mL.

CL_{renal} will be calculated accordingly:

$$\text{Single dose: } CL_{renal} = \frac{A_e}{AUC_{0-end of dosing interval}}$$

$$\text{Steady state: } CL_{renal} = \frac{A_e}{AUC_{0-tau}}$$

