Data based on [population]. Individual values under LLOQ are excluded from the figure. LLOQ is xx (unit). See listing 16.2.5-1 for a per subject LLOQ summary. lin: Linear. SAS program: [PROGRAM NAME].sas. Dataset version: ADXX YYYY-MM-DDTHH:MM:SS. Run by: [USERNAME] YYYY-MM-DDTHH:MM:SS. EDC data extracted: YYYY-MM-DDTHH:MM:SS.

Figure PC 14 Individual plasma concentrations of IRL757 over time 0-48h by subject (lin-lin) - SAD sub-study: food interaction (Full analysis set)

Example figure. Note that the numbers do not reflect real data. This template figure will be adjusted as needed depending on the collected data.

Data based on [population]. Individual values under LLOQ are excluded from the figure. LLOQ is xx (unit). See listing 16.2.5-1 for a per subject LLOQ summary. SAS program: [PROGRAM NAME].sas. Dataset version: ADXX YYYY-MM-DDTHH:MM:SS. Run by: [USERNAME] YYYY-MM-DDTHH:MM:SS. EDC data extracted: YYYY-MM-DDTHH:MM:SS.

Figure PP 1 Mean amount excreted in urine (Ae) over time for IRL757 - SAD (Pharmacokinetic analysis set)

Example figure. Note that the numbers do not reflect real data. This template figure will be adjusted as needed depending on the collected data.

[figure not shown]
Data based on [population]. Individual values under LLOQ are excluded from the figure. LLOQ is xx (unit). See listing 16.2.5-1 for a per subject LLOQ summary. lin: Linear. SAS program: [PROGRAM NAME].sas. Dataset version: ADXX YYYY-MM-DDTHH:MM:SS. Run by: [USERNAME] YYYY-MM-DDTHH:MM:SS. EDC data extracted: YYYY-MM-DDTHH:MM:SS.

Figure PP 2 Mean amount excreted in urine (Ae) over time for 3 main metabolites -SAD (Pharmacokinetic analysis set)

Same layout as Figure PP 1

Figure PP 3 Mean fraction excreted (Fe) over time for IRL757 - SAD (Pharmacokinetic analysis set)

Same layout as Figure PP 1

*10.3.1.2 Dose proportionality analysis***Figure PP 4 Dose proportionality for Cmax - SAD (Pharmacokinetic analysis set)**

Example figure. Note that the numbers do not reflect real data.

Include a footnote with the regression equation. Include a footnote with the 90% CI for the slope parameter/coefficient in the model, the calculated acceptance region described in Section 9.2.1.1 and the conclusion of dose-proportionality/non-dose-proportionality. It will also be specified in the footnote which data are used.

Figure PP 5 Dose proportionality for AUC_{0-inf} - SAD (Pharmacokinetic analysis set)

Same layout as Figure PP 4

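### The mean urine Ae and Fe figures exclude values below LLOQ, and SAP 5.7 has no urine rule; per-fraction means in late fractions would be biased upward

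*SAP*

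**What the plan says.** SAP 5.7 sets the default: "Generally, no imputation of data will be performed". It then makes two LLOQ/2 exceptions. One is for plasma: "when calculating statistics for PK plasma concentrations, concentrations under LLOQ will be replaced with LLOQ/2 if more than 50% of the values" at a time point are quantifiable. The other is for the safety laboratory: "Safety laboratory concentrations under LLOQ will be replaced with LLOQ/2". Urine is not mentioned. The only figure rule in that section is: "For figures presenting individual PK concentrations, no imputation is performed for values under LLOQ".

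SAP 9.2.1 has a separate rule for deriving PK parameters, under which BLQ values before Cmax count as zero and "Concentrations below LLOQ occurring after C_{max} will be omitted from the analysis". The same section defines total Ae as volume times concentration added over fractions: "The A_e over 0-12 hours (MAD BID), 0-24 hours (SAD 1-4) and 0-48 hours (SAD 5) is the sum of all intervals".

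In SAP 10.3.1.1 and again in 11.3.1.1, Figure PP 1 plots mean Ae against time and carries the footnote "Individual values under LLOQ are excluded from the figure". Figures PP 2 (metabolite Ae) and PP 3 (Fe) are told to follow its layout. The mean plasma figures (Figure PC 1 in both parts) have no such sentence; the individual plasma plots do.

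**The concern.** A BLQ urine fraction with a recorded volume is not missing. It shows that the subject excreted no more than volume x LLOQ in that interval. Dropping it from a mean leaves the average to the subjects who still excrete measurable drug, and the plotted value then describes a selected subgroup whose size changes from one fraction to the next.

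Ae and Fe are named secondary endpoints, and these figures are where a reader will look at the time course of urinary excretion. BLQ values are expected mainly in the late fractions, so the tail of the curve would look higher than it is. The SAP offers no other urine rule to fall back on: the parameter rule in 9.2.1 is tied to Cmax, which a urine fraction does not have.

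**Working it through.** The documents give no figure on this point to reproduce.

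**Inputs from the documents.** Active subjects per cohort: 6 in SAD, 9 in MAD (protocol synopsis). SAD fractions: 0-6, 6-12 and 12-24 h, plus 24-48 h in cohort 5 only (protocol Table 3). MAD fractions on Day 10: 0-8, 8-12 and 12-24 h (protocol Table 7). Expected half-life: 2-7 h (synopsis). LLOQ and BLQ rate: not given.

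**1. Exclusion against BLQ counted as zero.** With k of n subjects BLQ, the ratio of means is n/(n-k).

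- n = 6: 6/5 = 1.20, 6/4 = 1.50, 6/3 = 2.00 for k = 1, 2, 3.
- n = 9: 9/8 = 1.13, 9/7 = 1.29, 9/6 = 1.50, 9/5 = 1.80 for k = 1 to 4.
- k = 0: ratio 1, no effect.

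**2. Exclusion against LLOQ/2.** Let the quantifiable values average m x LLOQ, with equal volumes. The ratio is n x m / [(n-k) x m + 0.5 x k]. For m from 1.5 to 10:

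- n = 6: 1.12-1.19 (k = 1) to 1.50-1.90 (k = 3). Example with k = 3, m = 1.5: 9/(4.5 + 1.5) = 1.50.
- n = 9: 1.08-1.12 (k = 1) to 1.42-1.73 (k = 4). Example with k = 4, m = 10: 90/(50 + 2) = 1.73.

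**3. Exclusion against the true mean.** With equal volumes the bias is always upward, because every dropped Ae lies below every retained one. With unequal volumes a dilute, large BLQ fraction could exceed a small quantifiable one, so the direction then holds on average. An illustrative simulation used the SAD fractions, n = 6 and 9, first-order elimination and half-life log-uniform over 2-7 h. Assumed, and not in the documents: log-SD 0.3 on renal clearance and on volume, mean volumes 0.5, 0.5, 0.8 and 1.6 L, and LLOQ at 0.1%, 1% or 5% of the mean 0-6 h urine concentration. Exclusion means are taken over runs with at least one quantifiable value.

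| Fraction | LLOQ | BLQ | Exclusion / true | LLOQ/2 / true |
|---|---|---|---|---|
| 12-24 h | 0.1% | 0% | 1.00 | 1.00 |
| 12-24 h | 1% | about 7% | 1.06-1.07 | 1.00 |
| 12-24 h | 5% | 38% | 1.48 | 1.01 |
| 24-48 h | 0.1% | 29% | 1.40 | 1.00 |
| 24-48 h | 1% | 61% | 2.3 | 1.12 |
| 24-48 h | 5% | 92% | 4.2 | 2.0 |

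Fractions 0-6 and 6-12 h gave 1.00-1.01 under exclusion throughout.

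**4. If the figures are cumulative.** Dropping a subject's point when the current fraction is BLQ gave 1.00-1.23 times truth at 24 h and 1.17-1.88 at 48 h. Keeping the subject and adding nothing for the BLQ fraction gave 0.97-1.00.

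**5. How much of the total is at issue.** Under first-order elimination the 12-24 h share of 0-24 h excretion is x/(1+x), with x = 2^(-12/half-life). At 2 h, x = 1/64 and the share is 1/65 = 1.5%. At 4 h, x = 1/8 and it is 1/9 = 11%. At 7 h, x = 0.305 and it is 0.305/1.305 = 23%. A large relative error in a late fraction can therefore be a small part of total Ae.

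**The case against.** The best defence is that the footnote is leftover template text. It repeats the wording of the individual plasma plots, explains an axis abbreviation that belongs to concentration plots, and refers to Listing 16.2.5-1, which holds plasma data; urine is in 16.2.5-2. The figure is marked as an adjustable template, and all urine concentrations will be listed. This is probably how the sentence got there. It does not remove the point: the sentence stands in both parts, it is the only stated handling of BLQ urine values, and Section 5.7 supplies nothing to override it.

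Three stronger readings are tempting, and the documents do not support them.

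- *The urine tables also exclude BLQ values.* A reader might infer this from the n/BLQ rows in MAD Tables PP 3 and PP 7. Plasma Table PC 1 has the same rows, and there LLOQ/2 is imputed. The urine tables do ask for geometric means, which cannot take a zero, so they need a rule; they do not say which. The SAD tables were not available to check.
- *Total Ae, Fe and renal clearance are biased upward.* That requires one BLQ fraction to make a subject's total missing, which the SAP does not say. Leaving the fraction out of the sum gives a small downward error (0.97-1.00 of truth in step 4). In MAD, total Ae stops at 12 h, so the 12-24 h fraction does not enter it.
- *Comparison between dose levels is distorted.* This depends on BLQ rates by dose, which are unknown. The 24-48 h fraction, where the simulated effect is largest, is scheduled only for SAD cohort 5.

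**Conclusion.** The point holds as a minor one. The SAP lacks a urine BLQ rule, and the sentence printed under the mean urine figures is wrong for a mean. Read literally as per-fraction means, late fractions are overstated: by a factor of 1.2 to 2.0 relative to BLQ as zero with 1 to 3 of 6 subjects BLQ, and 1.13 to 1.80 with 1 to 4 of 9. The effect is nil if nothing is BLQ and close to nil in the early fractions. The size against the true mean rests on an assumed LLOQ and assumed variability, so the simulated factors are illustrations and not predictions. The figures are descriptive displays of secondary endpoints. Nothing here touches the primary safety endpoints or the dose-proportionality tests, which use plasma AUC and Cmax.

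**What to change.** 1. In Figures PP 1-3, SAD and MAD, delete the exclusion sentence, refer to Listing 16.2.5-2, and state whether the plotted values are per fraction or cumulative. MAD Tables PP 3 and PP 7 need the same listing correction.
2. Add a urine rule to SAP 5.7 with two parts:
   - *Per-interval statistics and mean figures:* set a BLQ urine concentration to LLOQ/2 (Ae = volume x LLOQ/2) when more than 50% of the values in that interval are quantifiable; otherwise report NC. The urine tables now print NC only when more than half are BLQ, so an exact half (3 of 6) needs aligning.
   - *Each subject's total Ae, Fe and renal clearance:* keep the subject and apply one fixed value to every BLQ fraction, whatever the other subjects show. Zero is one option, with LLOQ/2 as a sensitivity analysis. The 50% condition must not be used here, because it would make one subject's total depend on the others.

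The cost is a short paragraph and a footnote edit, with no new data. Zero and LLOQ/2 are both approximations. In the table above LLOQ/2 was within about 1% of truth wherever most values were quantifiable. Under other assumptions (7 h half-life, CV 30% on rate constant and renal fraction, CV 40% on volume, 11-44% BLQ, 12-24 h fraction) it understated the mean by 2-9%, against a 5-17% overstatement from exclusion.

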A Follow-up Visit will be performed for all subjects 5-10 days after last administration of IMP.

In the food interaction sub-study, each subject's involvement duration will also depend on how soon the second dose will be given after the first IMP administration (may vary between 5 half-lives and 14 days).

Total duration of involvement per subject:

- SAD part of the trial: from 7 days up to 39 days
- food interaction sub-study: up to 54 days
- MAD part of the trial: from 16 days up to 48 days

Statistical methods

No formal sample size calculation has been performed for this trial. The size of the cohorts/dose groups is considered sufficient to provide adequate information on the safety and PK parameters for the purpose of this trial.

All statistical calculations will be performed using the SAS® version 9.4 or later program (SAS Institute Inc., Cary, NC, USA). The statistical analyses will only include descriptive statistics reflecting the explorative nature of the trial. In general, the data will be presented by treatment and dose group. The data for subjects receiving placebo will be presented pooled across groups.

Continuous data will be summarised by treatment and dose group using number of observations, mean, standard deviation (SD), median, minimum and maximum. Categorical data will be summarised by treatment and dose group using the number and percentage of subjects in each category.

Unless otherwise stated, statistical evaluations will be based on all subjects who have received randomised treatment with IMP and have available data. Evaluations will be done according to actual treatment regardless of randomisation. A dose group will consist of all subjects treated with that dose

regardless of dose panel. Similarly, the placebo group will consist of all subjects treated with placebo regardless of dose panel. The Full Analysis Set (FAS) data set will be used for the safety and tolerability assessments.

The Per Protocol Analysis Set (PPAS) comprises data from all subjects randomised and treated with evaluable PK parameter data, and no major protocol deviations with an impact on PK data. The PPAS set will be used for presentation of PK endpoints.

The PK parameters will be calculated by non-compartmental analysis (NCA) using the software Phoenix WinNonlin® version 8.3 or later (Certara, USA).

Table 3 Schedule of events, SAD part of the trial (fasted condition)

Visit	Visit 1	Visit 2				Follow-up Visit
Day	Screening	In-clinic				Ambulatory

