5 STATISTICAL AND ANALYTICAL PLANS

5.1 Statistical hypotheses

The primary objective of this trial is to assess safety and tolerability, and no hypothesis testing will be conducted on data related to these endpoints. Additionally, as part of the secondary objectives and endpoints, this trial aims to test the hypothesis that pharmacokinetic AUC and C_{\max} are proportional to the dose administered. Please refer to sections 9.2.1.1-9.2.1.2 below for more details about the dose proportionality analyses.

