5.6 Significance level

All statistical hypotheses in this trial will be answered using two-sided 90% confidence intervals.

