9.2.1.1 Dose proportionality analysis - SAD

Dose-proportionality (an increase in dose corresponds to a proportional increase in PK outcome) after a single dose, will be assessed using the power model, i.e., linear regression modelling of $AUC_{0-\infty}$ and C_{\max} respectively on log-scale according to the formula:

$$\ln(PK) = \beta_0 + \beta_1 \times \ln(dose)$$

Let h be the highest dose and l be the lowest dose. Then the predicted PK geometric mean (back-transformed to normal scale) of the high dose is $e^{\beta_0} h^{\beta_1}$, and that of the low dose is $e^{\beta_0} l^{\beta_1}$. Let r be the maximal dose ratio, i.e., h/l . Dose proportionality corresponds to:

$$e^{\beta_0} h^{\beta_1} / e^{\beta_0} l^{\beta_1} = h/l \rightarrow (h/l)^{\beta_1-1} = r^{\beta_1-1} = 1$$

Let $\Theta_L=0.8$ and $\Theta_H=1.25$ be the lower and upper acceptance limits respectively, (0.8 and 1.25 being the industry standard limits). Dose-proportionality occurs when

$$\Theta_L < r^{\beta_1-1} < \Theta_H,$$

which on natural log scale equates to

$$\ln(\Theta_L) < (\beta_1 - 1)\ln(r) < \ln(\Theta_H) \rightarrow 1 + \frac{\ln(\Theta_L)}{\ln(r)} < \beta_1 < 1 + \frac{\ln(\Theta_H)}{\ln(r)}$$

Specifically, dose-proportionality is declared when the 90% CI for β_1 from the linear regression model on log scale lies entirely within the acceptance region:

$$\left[1 + \frac{\ln(0.8)}{\ln(r)}, 1 + \frac{\ln(1.25)}{\ln(r)} \right]$$

Dose proportionality analysis will include all the SAD fasted cohorts (including data from the fasting part of the sub-study).

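### The dose-proportionality footnotes report failure to show equivalence as non-proportionality; how often this would mislabel a proportional drug depends on a CV the plan does not give

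*SAP*

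**What the plan says.** SAP 9.2.1.1 regresses ln(PK) on ln(dose) for AUC0-inf and Cmax. Proportionality is declared when the 90% CI for the slope β1 "lies entirely within the acceptance region", which runs from 1 + ln(0.8)/ln(r) to 1 + ln(1.25)/ln(r), where r is the highest dose divided by the lowest. The limits are justified as "0.8 and 1.25 being the industry standard limits". The section does not say what to conclude when the interval is not inside.

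The figure shells fill that gap. In SAP 10.3.1.2 (SAD) and 11.3.1.2 (MAD), the Figure PP 4 footnote must give the regression equation, the 90% CI for the slope, and "the calculated acceptance region described in Section 9.2.1.1 and the conclusion of dose-proportionality/non-dose-proportionality". Figure PP 5 uses the same layout.

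SAP 5.1 states that "this trial aims to test the hypothesis that pharmacokinetic AUC and" Cmax are proportional to dose, and SAP 5.6 adds that "All statistical hypotheses in this trial will be answered using two-sided 90% confidence intervals". SAP 5.2 confirms that no sample size calculation was done. Dose proportionality is a named secondary endpoint for both parts (Protocol synopsis, Endpoints; SAP Table 1).

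**The concern.** The rule in 9.2.1.1 is an equivalence test. Passing it supports proportionality within the limits. Failing it can mean either that the slope departs from 1 or that the interval is too wide to tell. The footnote wording merges these two cases under the label of non-proportionality, so an interval centred on a slope of exactly 1 but slightly wider than the region would be reported as a negative finding. This is a fault of logic at any sample size.

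How often it would matter depends on precision, and the cohorts are small: six active subjects per SAD level and nine per MAD level. At stake is a wrong statement on a secondary endpoint. The primary safety endpoints and the data collected are not affected.

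**Working it through.** The plan gives no power figure or CV for this analysis, so there is nothing of its own to reproduce. The check is how often the stated rule would give each label if the true slope were 1.

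**Inputs from the documents**
- SAD: 5 levels × 6 active = 30 (Protocol synopsis, Methodology). The fasted arm of the food sub-study adds 6 (SAP 9.2.1.1), giving 36.
- MAD: 9 active per level, analysed only with three or more levels (SAP 9.2.1.2), so 27 with three.
- Two-sided 90% CI; limits 0.80 and 1.25, that is ±ln(1.25) = ±0.2231 on the scale of (β1−1)·ln(r).

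**Assumptions (not in the documents)**
- Even log spacing of doses, sub-study dose at level 4, true slope 1, log-normal error, and a range of between-subject CVs with σ = √ln(1+CV²).

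**Step 1: the dose range cancels.** Rescale ln(dose) to run from 0 to 1 and let K = Σ nᵢ(xᵢ − x̄)². Then SE(β1) = σ/(ln r·√K), and the region for β1 is 1 ± 0.2231/ln r. Both scale with 1/ln r, so with fixed relative spacing r drops out. Check at r = 16: 0.2231/2.7726 = 0.0805, giving a region of 0.9195 to 1.0805.

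**Step 2: K and half-width on the ln-ratio scale** (t(0.95, N−2)·σ/√K)
- SAD n=30: K = 3.75, half-width 0.878σ.
- SAD n=36: Σnx = 19.5 and Σnx² = 14.625, so K = 14.625 − 19.5²/36 = 4.0625; half-width 0.839σ.
- MAD 3×9: K = 4.5, half-width 0.805σ.

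**Step 3: the largest CV at which the CI can fit with a slope estimate of exactly 1.** Set the half-width to 0.2231: σ = 0.254, 0.266 and 0.277, so CV = √(exp(σ²)−1) = 25.8%, 27.1% and 28.3%.

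**Step 4: probability of each label.** Proportionality is declared if |estimate| + t·SE(estimated) < 0.2231. This was integrated over the chi-square distribution of the residual variance. A 40,000-run simulation agreed (0.436 against 0.439 at CV 20%, SAD n=36).

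| CV | σ | Half-width, SAD n=36 | Declared proportional, SAD n=36 | Labelled non-proportional, SAD n=36 | Same, SAD n=30 | Same, MAD 3×9 |
|---|---|---|---|---|---|---|
| 10% | 0.100 | 0.084 | 99% | 1% | 1% | <1% |
| 15% | 0.149 | 0.125 | 81% | 19% | 24% | 15% |
| 20% | 0.198 | 0.166 | 44% | 56% | 63% | 50% |
| 25% | 0.246 | 0.207 | 14% | 86% | 90% | 80% |
| 30% | 0.294 | 0.246 | 2% | 98% | 98% | 95% |

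**Step 5: would the data support the label?** In the same simulation (SAD n=36), the CI lay wholly outside the region in fewer than 0.1% of trials at CV 20% and about 0.1% at CV 30%. At CV 30% the CI contained a slope of 1, yet failed the rule, in 88% of trials. That is about 90% of those labelled non-proportional (0.879/0.979).

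**Step 6: sensitivity.** For SAD n=36, the CV at which a proportional drug has an even chance of being declared proportional is 19% in the base case. It falls to 16% if the middle doses cluster and rises to 27% if the doses bunch at the two extremes. A sixth, evenly spaced SAD level gives 48% declared at CV 20% and 3% at CV 30%. A fourth MAD level gives 59% and 7%.

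**The case against.** A reader might infer that a proportional drug will usually be called non-proportional because the interval cannot fit at this sample size. The documents do not support that. They give geometric CV only as an output, and the doses are redacted and tentative. At CV 10% the rule almost always succeeds, and at 15% it succeeds in 76% to 85% of trials across the three designs tabulated. The interval is ruled out regardless of the estimate only above an observed CV of about 26–28%. Spacing, the sub-study dose level and optional cohorts all move the figures, and with only two MAD levels that analysis is not run.

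A reader might also infer that the label will steer later dose selection. Neither document says so, and escalation within the trial rests on the safety review committee's assessment of PK and safety data after each level.

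Two further objections have force. The two-way wording sits in a figure shell, while 9.2.1.1 is silent on what failure means. And the footnote prints the equation, the CI and the region, so a careful reader can see when a result is merely imprecise. This reduces the harm, but the SAP still requires "the conclusion of dose-proportionality/non-dose-proportionality" beside an interval that may support neither.

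Finally, the protocol's statement that "The statistical analyses will only include descriptive statistics reflecting the explorative nature of the trial" sits awkwardly with the hypothesis in SAP 5.1. That is a separate discrepancy and does not bear on the two-way label.

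**Conclusion.** The concern stands in conditional form. The reporting rule is wrong as written at any CV, because it offers no outcome for an interval that is neither wholly inside nor wholly outside the region. Its practical size is unknown until the CV is known. Under even log spacing and a true slope of 1, mislabelling is rare at CV 10%, about as likely as not near CV 19–20%, and nearly certain at 30%, for SAD and MAD alike. These are scenario figures, not predictions for this drug. The extra cohorts examined do not rescue the rule at CV 30%.

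**What to change.** In SAP 9.2.1.1, and in the PP 4 and PP 5 footnotes of 10.3.1.2 and 11.3.1.2, replace the two-way conclusion with three outcomes:
- *proportional*, if the 90% CI is wholly inside the acceptance region;
- *departure from proportionality*, if it is wholly outside;
- *inconclusive*, otherwise.

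Report r^(β1−1) with its 90% CI next to the slope, so that the result reads directly against 0.80 and 1.25. Make the change before unblinding, so that the label is not chosen with the results in view.

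Under the base-case SAD assumptions, a proportional drug would then be reported as proportional, inconclusive or departing in about 44%, 56% and under 0.1% of trials at CV 20%, and in about 2%, 98% and 0.1% at CV 30%.

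The cost is a few sentences and a footnote, with no new data. The downside is that the report may say 'inconclusive'. Two additions are optional: giving the largest dose ratio over which the CI stays within 0.80 to 1.25, and rewording SAP 5.1 as estimation.
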